4.3.1.1. Supportive Analysis: Analysis of Covariance

An additional analysis of change from baseline at Day 28 will be performed using the ANCOVA model for the ITT and PP populations. This model will include the change from baseline at Day 28, strata, and treatment group (plus an interaction term strata*treatment).

4.3.2. Graphical Analysis of Weekly In-clinic Blood Pressure

Mean blood pressure (\pm standard error of the mean [SEM]) at each visit will be graphed with separate lines for each treatment group. In addition, the mean (SEM) change from baseline will be graphed. Least squares means will be graphed in similar fashion.

4.3.3. Ambulatory Blood Pressure

The analysis of ABP will be modeled in 3 ways. The first will compare the change in average daytime (8 AM to 4 PM) values of diastolic and systolic blood pressure at baseline to the average values post-baseline using an ANCOVA model with stratification and treatment included in the model. Means and LS means will be reported. All analyses will be performed using the ABPM population.

In addition to the results of the model, mean hourly results, daytime(8 AM to 4 PM), nighttime (10 PM to 6 AM), and 24-hour results will be summarized by treatment group.

This ANCOVA model will also be performed separately for the pre-hypertensive and Stage 1 subjects.

The second method will use piecewise linear functions (linear splines) in which linear slopes of each subject's values over time at baseline and post-baseline periods are calculated. The first "knot" will be placed at the time of treatment and additional knots will be evaluated graphically using lowess smoothing curve graph to determine a second inflection point of non-linearity. By calculating the coefficient of each spline, the rate of change in ABP can be calculated and compared between treatment groups.

ABP will also be analyzed by Dippers and Non-Dippers based on the American Heart Association classification using systolic blood pressure. Dippers and Non-Dippers are defined as follows:

Dipper: 10% decrease in nighttime SBP versus daytime SBP
Non-Dipper: <10% decrease in nighttime ambulatory SBP versus daytime ambulatory SBP.

The shift in dipping classification from baseline to day 28 will be tabulated.

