2. SUBJECT POPULATION

2.1. Population Definitions

The following subject populations will be evaluated and used for presentation and analysis of the data:

- Intent-to-Treat (ITT) Population: Includes all randomized participants. Subjects will be analyzed according to the treatment assigned by the randomization schedule. The ITT population will be the primary population for efficacy analyses.
- Safety Population: Includes all subjects who received at least 1 dose of study medication. Subjects will be analyzed according to the study drug received.
- Per Protocol (PP) Population: Subjects who have baseline and Day 28 post-baseline in-clinic systolic or diastolic blood pressure measurement, and did not have any major protocol violations which could potentially compromise interpretation of results. The PP population will be used for supportive summaries of efficacy data.
- Ambulatory Blood Pressure Monitoring Population (ABPP): Subjects in the Safety population who had valid baseline and Day 28 ambulatory blood pressure monitoring (ABPM) measurements. Subjects who repeated the ABPM are included in the population if the repeated assessment met the device monitor's criteria for "passing."

The ITT population is the primary population for the analysis of efficacy parameters. A subset of efficacy parameters will be evaluated for the PP population (see [Section 4.3](#)). The Safety population is the primary population for the analysis of safety endpoints.

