3.2. General Methods

The analyses will be conducted on all participant data when the trial ends. Data will be presented by treatment arm and overall except where noted. Listings will be sorted by treatment, strata, and subject.

Analysis of the change from baseline in systolic and diastolic blood pressure will be performed using a both mixed-effects model repeated measures (MMRM) and an analysis of covariance (ANCOVA). Least squares (LS) means, confidence interval (CI) on the means, and p-values from the model will be presented. In addition, descriptive statistics on the actual values and the change from baseline will be presented for the 4-spray B244 arm, the 8-spray B244 arm, and the placebo arm.

Categorical variables will be summarized by frequency distributions (number and percentages of subjects) and continuous variables will be summarized by descriptive statistics (mean, SD, etc).

Adverse events will be summarized by treatment using the Medical Dictionary for Regulatory Activities (MedDRA) system organ class (SOC) and preferred term. Separate tabulations will be produced for all treatment-emergent AEs (TEAEs), treatment-related AEs (those considered by the Investigator as at least possibly drug-related), and AEs with Grade 3 or higher severity. By-subject listings will be provided for any deaths, SAEs, and AEs leading to discontinuation.

Descriptive statistics for each treatment arm will be provided for clinical laboratory values (eg, serum chemistry) and vital signs data, presented as both actual values and changes from baseline relative to each on-study evaluation. Out of range clinical laboratory values will be listed.

All data will be provided in by-subject listings.

All data listings that contain an evaluation date will contain a relative study day (Rel Day). Pre-treatment and on-treatment study days are numbered relative to the day of the first dose of study medication which is designated as Day 1. The preceding day is Day -1, the day before that is Day -2, etc.

All output will be incorporated into Microsoft Word or Excel files, or Adobe Acrobat PDF files, sorted and labeled according to the International Conference on Harmonisation (ICH) recommendations, and formatted to the appropriate page size(s).

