4.3.1. Weekly In-Clinic Blood Pressure

To assess treatment effect, change from baseline in weekly systolic and diastolic blood pressure values will be analyzed using a mixed effect model that includes the change from baseline at Days 7, 14, 21, and 28. Day 42 will not be used in the primary endpoint analysis. The model will include stratification factors of spray number and hypertension and baseline blood pressure as covariates, with treatment group (B244 or placebo) and visit as fixed effects, and subject as a random effect. The model will include the following interaction terms: treatment*visit, strata*visit, treatment*strata, and treatment*strata*visit. Estimates of the adjusted LS mean, difference in LS means, and corresponding 95% CIs will be obtained from the model.

Linear contrasts of the differences between each treatment group (4 doses or 8 doses) and placebo at each visit will be used to compare the results between treatments using LS means between each active treatment group and placebo. Nominal 2-sided p-values and 95% CIs will be reported at Days 7, 14, 21, and 28.

Treatment group comparisons within each strata will be an exploratory analysis.

Mixed models will be implemented using PROC Mixed in SAS, using an unstructured within-subject covariance matrix and denominator degrees of freedom from the Kenward-Roger method. Other covariance matrices (first order autoregressive process [AR(1)], compound symmetry, independent) may be utilized in the event that the unstructured matrix does not converge. In this event, the matrix structure that converges provides the lowest akaike information criterion (AIC) value will be selected.

This modeling will be performed for both systolic and diastolic blood pressure, in both the ITT and PP populations.

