Source: [Listing 16.2.6.1](#)

PROGRAM NAME: XXXXXXXXXXXXXXXXXXXXXXXXXXXXXXXXXXXXXXX

DATE: HH:MM/DDMMYYYY

PROGRAMMING NOTE: Continue for Diastolic Blood Pressure Mixed Model Analysis.

Repeat Table 14.2.1A for:

Table 14.2.1B Summary of Values and Change from Baseline for Systolic and Diastolic Blood Pressure - Mixed Model Analysis (PP Population)

Table 14.2.1C Summary of Values and Change from Baseline for Systolic and Diastolic Blood Pressure by Race - Mixed Model Analysis (ITT Population)

Table 14.2.1D Summary of Values and Change from Baseline for Systolic and Diastolic Blood Pressure by Hypertension Stage - Mixed Model Analysis (ITT Population)

Table 14.2.1E Summary of Values and Change from Baseline for Systolic and Diastolic Blood Pressure by Gender - Mixed Model Analysis (ITT Population)

Table 14.2.1F Summary of Values and Change from Baseline for Systolic and Diastolic Blood Pressure by Age Group - Mixed Model Analysis (ITT Population)

PROGRAMMING NOTE: Replace Visit with each subgroup as applicable per table title. P-values and LSMEANS are not required for any subgroups except hypertension stage.

Table 14.2.2A

Change from Baseline at Day 28 ANCOVA Model for Systolic and Diastolic Blood Pressure (ITT Population)

Parameter: Systolic Blood Pressure

		B244			
Visit	Statistic	4 Sprays (N=xx)	8 Sprays (N=xx)	All B244 (N=xx)	Placebo (N=xx)
Day 28	LS Mean (SE)	xx.x (xx.xx)	xx.x (xx.xx)	xx.x (xx.xx)	xx.x (xx.xx)
	95% CI	xx.x	xx.x	xx.x	xx.x
	LS Mean Difference (SE) (Placebo-Active)	xx.x (xx.xx)	xx.x (xx.xx)	xx.x (xx.xx)	
	95% CI for Mean Difference	Xx, xx	Xx, xx	Xx, xx	
	P-value (vs Placebo)	0.xxxxx	0.xxxxx	0.xxxxx	
	P-value (vs 8 Spray)	0.xxxxx			

LS: Least-squares. SE = Standard Error. CI = Confidence Interval.

Model: The ANCOVA model includes the change from baseline as the dependent variable, treatment and strata as factors and baseline value as a covariate.

Source: [Listing 16.2.6.1](#)

PROGRAM NAME: XXX

DATE: HH:MM/DDMMYYYY

PROGRAMMING NOTE: Continue for Diastolic Blood Pressure.

Repeat for:

Table 14.2.2B Change from Baseline at Day 28 ANCOVA Model for Systolic and Diastolic Blood Pressure (PP Population)

Table 14.2.2C Change from Baseline at Day 28 ANCOVA Model for Systolic and Diastolic Blood Pressure by Hypertension Stage (ITT Population)

Table 14.2.3A

Summary of Values and Change from Baseline for Ambulatory Blood Pressure (ABP Population)

Parameter: Systolic Blood Pressure

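### The ambulatory BP analysis names no baseline covariate, plans no treatment difference for nighttime or 24-hour BP, and is described as ANCOVA in one place and a mixed model in others

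*SAP*

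**What the plan says.** **Daytime model.** SAP 4.3.3 compares change in average daytime systolic and diastolic BP "using an ANCOVA model with stratification and treatment included in the model". It promises means and LS means, and adds: "This ANCOVA model will also be performed separately for the pre-hypertensive and Stage 1 subjects". The analysis population consists of "Subjects in the Safety population who had valid baseline and Day 28 ambulatory blood pressure monitoring (ABPM) measurements".

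**Nighttime and 24-hour.** The same section says "nighttime (10 PM to 6 AM), and 24-hour results will be summarized by treatment group". Protocol 4.2 and SAP 1.1.2.2 list both as secondary objectives comparing B244 with vehicle.

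**In-clinic analyses, for comparison.** For the mixed model, SAP 4.3.1 states: "The model will include stratification factors of spray number and hypertension and baseline blood pressure as covariates". The footnote to the in-clinic ANCOVA shell (Table 14.2.2A) has "treatment and strata as factors and baseline value as a covariate". The text for that same ANCOVA, SAP 4.3.1.1, reads: "This model will include the change from baseline at Day 28, strata, and treatment group (plus an interaction term strata*treatment".

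**Method.** SAP 3.2 analyses change in BP "using a both mixed-effects model repeated measures (MMRM) and an analysis of covariance (ANCOVA"), with CIs and p-values. SAP 3.10 makes MMRM the primary analysis for primary and secondary endpoints. Protocol 15.3.8 carries its mixed model over to ambulatory assessments. Tables 14.2.4A to C have mixed-model titles.

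**The concern.** A programmer who follows 4.3.3 literally would fit change in ambulatory BP on treatment and strata alone. The estimate would be less precise than it need be, and a chance baseline imbalance would be corrected only as far as the hypertension stratum reflects it. In the separate pre-hypertensive and Stage 1 runs the hypertension factor is constant, so no BP adjustment is left.

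Two stated objectives against vehicle could also reach the report with group means and no estimated difference. For daytime BP, the model type, covariates and output are not fixed consistently. SAP 3.7 makes no multiplicity adjustment, so a single model fixed in advance is the main protection against choosing among alternatives later.

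**Working it through.** **1. Is a baseline term supplied elsewhere for ambulatory BP?** No.
- SAP 3.6 lists race, BMI category and smoking status, for exploratory use.
- SAP 4.3.5 allows baseline factors only in the 4.3.1 models.
- No ambulatory table shell carries a model footnote.

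**2. Which method applies?** SAP 4.3.3 names ANCOVA. SAP 3.10, Protocol 15.3.8 and the titles of Tables 14.2.4A to C indicate a mixed model. SAP section 5, which lists changes from the protocol, is silent on ambulatory modelling. Protocol 12.3.1 provides two ABPM sessions, hence one post-baseline session and one Day 28 value per window mean. For a window mean, an MMRM therefore has no repeated visits and reduces to an ANCOVA-type model.

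**3. What do the table shells hold?**
- 14.2.3A to E: n, mean (SD), median and range.
- 14.2.4A to C: the same statistics by hour, despite their titles.
- 14.2.5: counts.
- None has an LS mean, difference, CI or p-value. In-clinic Tables 14.2.1A and 14.2.2A have all four.

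**4. The plan's own figure.** SAP 3.1 takes 52 per arm, a difference of 5.8 and a two-sided alpha of 0.05. A t-test then gives 79.7% power at SD 10.5 and 90.2% at SD 9, matching the stated 80% and 90%. These are for in-clinic systolic BP; no ambulatory power is given.

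**5. Size of the precision loss.**

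Assumptions:
- Baseline and Day 28 ambulatory means have equal variance (scaled to 1) and correlation r.
- The hypertension stratum has correlation ρ with baseline ambulatory BP and adds nothing once baseline is known.
- r runs from 0.5 to 0.9 and ρ from 0.4 to 0.8.
- The unadjusted SD of change is 10.5, borrowed from SAP 3.1.
- There are 49 per arm: 52 × 0.95 = 49.4, using the under-5% failure estimate in Protocol 12.3.4.

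Formulas:
- Var(change) = 2(1−r)
- Var(change | stratum) = 2(1−r) − ρ²(1−r)²
- Var(change | stratum, baseline) = 1−r²
- Ratio of the last to the second = (1+r) / (2 − ρ²(1−r))
- Unadjusted half-width = t(0.975, 94) × 10.5 × √(2/49) = 1.9855 × 2.1213 = 4.21 mmHg
- Stratum only = 4.21 × √(1 − ρ²(1−r)/2)
- With baseline = 4.21 × √((1+r)/2)

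| r | Further variance cut from baseline (ρ 0.8 to 0.4) | Half-width, stratum only | Half-width, with baseline | Gain (mmHg) |
|---|---|---|---|---|
| 0.5 | 11–22% | 3.86–4.13 | 3.65 | 0.21–0.48 |
| 0.7 | 6–13% | 4.00–4.16 | 3.88 | 0.12–0.28 |
| 0.8 | 4–9% | 4.07–4.18 | 4.00 | 0.07–0.18 |
| 0.9 | 2–4% | 4.14–4.20 | 4.11 | 0.03–0.09 |

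For one spray group (about 24.5) against pooled placebo (49), the unadjusted half-width is 1.9855 × 10.5 × √(1/24.5 + 1/49) = 5.16. At r = 0.5 it is 4.73–5.05 with stratum only and 4.47 with baseline.

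**6. Cross-check by simulation.** This used 104 subjects and SD of change 10.5. The stratum was cut at the median of a variable correlated 0.3 or 0.6 with baseline ambulatory BP. For r from 0.5 to 0.8, the mean SE was 2.00–2.06 with strata only and 1.80–1.97 with baseline added. The strata recover little of the gain.

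**7. Chance imbalance.** A within-stratum baseline difference d shifts the change-score comparison by (1−r)d. For d = 2 mmHg that is 1.0 mmHg at r = 0.5 and 0.4 mmHg at r = 0.8.

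**The case against.** - **Baseline may be implied.** The 4.3.3 wording does not say that stratification and treatment are the only terms, and ANCOVA suggests a covariate. SAP 4.3.1.1 is equally silent, yet its shell footnote includes baseline. This stands. A reader might infer deliberate exclusion, or a biased comparison; the documents support neither, since randomization protects the estimate on average. But no footnote fills the gap for ambulatory BP.
- **The size is assumed throughout.** This also stands. With equal variances and SD of change 10.5, the implied baseline SD is 10.5/√(2(1−r)): 16.6 mmHg at r = 0.8 and 23.5 at r = 0.9. The latter is hard to credit when eligible clinic systolic BP is 120–159. And ρ = 0.8 is about the ceiling for an even split of a normal variable (√(2/π) = 0.798). Both points weaken the low-gain entries rather than the direction.
- **A mixed model is feasible.** Two sessions might be read as ruling one out. They do not: Protocol 12.3.3 takes readings every 20 minutes, so repeated readings could be modelled. The single-value argument holds only for window means. Table 14.2.4A may have lost its model rows rather than been mistitled.
- **Nighttime and 24-hour LS means.** SAP 4.3.4 might be read as graphing LS means that have no model. Its sentence can equally be limited to modelled windows, and Protocol 15.3.8 does not confine its mixed model to daytime. The firm point is that 4.3.3 plans no window-mean difference for these two; its spline method compares slopes.
- **Endpoint status.** A reader might infer that two formal endpoints go untested. Protocol 5.2 lists daytime only and SAP 1.2.5 names no window, so their status under the testing rule in SAP 3.2 is unclear.
- **Figures.** The ambulatory figure images are not available, so the missing inference is verified for tables only.

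**Conclusion.** The point holds as a specification gap, not as a demonstrated wrong analysis. It does not touch the primary endpoint. Run as written, the daytime ANCOVA gives up a modest amount of precision: about 0.2 to 0.5 mmHg in the pooled half-width at r = 0.5, falling below 0.1 mmHg at r = 0.9. That range depends on equal variances, assumed r and ρ, and an SD borrowed from in-clinic BP.

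The gaps that need no assumption are that 4.3.3 plans no estimated difference for two objectives against vehicle, that the documents disagree on ANCOVA or mixed model, and that no ambulatory table shell has room for inference. A reader might infer that the model will be picked after seeing results. Nothing in the documents shows this; they merely leave it open.

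**What to change.** 1. In SAP 4.3.3, add the baseline mean ambulatory BP for the same window and pressure as a covariate. Run this ANCOVA on daytime, nighttime and 24-hour systolic and diastolic BP, reporting LS mean differences (B244 minus placebo) with 95% CIs.
2. In SAP 3.10 and section 5, state that window-mean ambulatory BP, with one Day 28 value per window, uses this ANCOVA. If a mixed model on hourly readings is also intended, specify it as secondary.
3. Add one inferential ambulatory table with a model footnote. Either retitle Tables 14.2.4A to C as descriptive or add their model rows.
4. If nighttime and 24-hour p-values are shown, label them nominal and align the testing statement in SAP 3.2. If these windows are meant to be descriptive only, say so in 1.2.5 and limit the LS means in 4.3.4 to daytime.
5. As a separate correction for in-clinic BP, reconcile SAP 4.3.1.1 (no baseline, strata-by-treatment interaction) with the Table 14.2.2A footnote (baseline, no interaction): include baseline and make one choice on the interaction. Use one direction of difference, since 14.2.2A has placebo minus active and 14.2.1A has B244 minus placebo.

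The cost is SAP and shell wording, one table and a few model runs on data already collected. No visit, sample size or clinical rule changes.

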### **11.6.3 Study Day 1B-Baseline visit**

This visit should occur between the hours of 8am +/- 2 hrs

- Remove ABPM machine and check on the readings to make sure equipment performed as expected.
- blood for biomarkers
- allocation of a randomized treatment kit number via IWRS
- delivery of the corresponding pack of Investigational Product
- obtain skin swab samples pre drug application
- Study counseling
- Provide subjects with study soap and shampoo

- Study diary
- first application of Investigational Product (under medical supervision)
- obtain study medication weight for Investigational Product compliance
- start AE monitoring

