### **12.3 ABPM Measurements**

### **12.3.1 ABPM monitoring schedule**

ABPM will occur twice during the study. Subjects should report to the office at 8 AM + 120 minutes such that they are hooked up and dosed as close to 8:00 A.M. as possible (window 6:00 AM – 10:00 AM).

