### **12.3.2 Office visit**

Subjects must arrive at the office for ABPM hookup NOT HAVING TAKEN that day's dose of study medication, and at an appropriate time so that ABPM hookup, dosing of study medication, and start of the ABPM test is at 8 AM + 120 minutes (window 6:00 AM – 10:00 AM). Subjects who are non-compliant will be rescheduled for the following day.

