### **12.3.4 ABPM technical success/failure criteria**

The following are the technical acceptance criteria against which subject ABPM data will be evaluated:

- Subject dosing of study medication must occur no earlier than 6:00 AM and no later than 10:00 AM.
- There should be at least one (1) manually initiated ABPM reading after dosing of study medication. If no manual post-dose reading was recorded, START TEST time will equal the 1st valid reading after dosing, provided that the reading occurs between 6:00 AM and 10:00 AM.
- There should be a final manual reading on or after 24 hours of recording. If a manual reading was not recorded, the first recording after 24 hours will be considered the last valid recording of the session.
- There must be at least one (1) valid reading per hour with the following possible exception: no more than three (3) non-consecutive hours with zero (0) valid readings during the recording period and two (2) consecutive hours with zero (0) valid readings during the recording period.

Failure to achieve any one of the above criteria will result in the ABPM being declared a technical failure.

If a subject has a technical failure on their repeat recording at Baseline, those subjects will be excluded from the study. However, if subjects passes their baseline and fails the final repeat recording, data will be included in the Office BP analysis but be excluded from the ABPM analysis. We would estimate that this will occur in less than 5% of patients.

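### The spline analysis of ambulatory BP compares slopes around an undefined time of treatment and does not address mean ABP; nighttime and 24-hour ABP have no specified level test

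*SAP*

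**What the plan says.** SAP 4.3.3 analyses ABP in three ways.

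- **First method.** The change in the daytime average (8 AM to 4 PM) is taken from baseline to the "average values post-baseline using an ANCOVA model with stratification and treatment included in the model". Nighttime and 24-hour results are to be summarised by group.
- **Second method.** Under a linear spline, "linear slopes of each subject's values over time at baseline and post-baseline periods are calculated". As for where the segments meet, the earliest join "will be placed at the time of treatment and additional knots will be evaluated graphically using lowess smoothing curve graph". From the coefficients, "the rate of change in ABP can be calculated and compared between treatment groups".
- **Third method.** Dipper and non-dipper classification, with a shift table.

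The recordings are described in the protocol. Section 12.3.1 states that "ABPM will occur twice during the study". The baseline monitor is removed at Day 1B, and the first application comes later in the same visit list (11.6.3). If the recording fails, Day 1B activities wait for a valid repeat (11.6.4). For a monitored day, 12.3.2 has the subject arrive undosed "so that ABPM hookup, dosing of study medication, and start of the ABPM test is at 8 AM", within a 6 to 10 AM window. Section 12.3.4 expects a manual reading after dosing; failing that, "START TEST time will equal the 1st valid reading after dosing".

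The secondary objectives (SAP 1.1.2.2) are reductions in mean daytime, nighttime and 24-hour pressure. SAP 3.2 promises formal two-sided 0.05 tests on the secondary efficacy endpoints.

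**The concern.** The objectives concern levels, and the spline compares slopes. Its anchoring point is also hard to locate in the data. The baseline recording contains no treatment. The Day 28 recording starts at about the morning dose, so a segment before that dose has essentially no readings.

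At stake is whether this method can say anything about the ABP objectives. Apart from the dipper table, it is the only ABP method in 4.3.3 not confined to daytime. If it does not measure level, the nighttime and 24-hour objectives have no specified test, although formal testing is promised for secondary endpoints.

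**Working it through.** **Inputs from the documents.** Two 24-hour recordings with a reading every 20 minutes (Protocol 12.3.1, 12.3.3); effect 5.8 mmHg, SD 10.5, 52 per arm, two-sided alpha 0.05 (SAP 3.1, 3.2). The effect and SD are in-clinic planning values and serve only to scale the illustration.

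**Assumptions.** SD of the true change in recording level 10.5 (range 8 to 11); reading noise SD 9; between-subject slope SD 0.3 mmHg/h (range 0.1 to 0.6); the same circadian curve in both recordings. Base case 2,000 simulated trials, variations 1,000.

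**Step 1: reproduce the plan's figure.** SE = 10.5 × √(2/52) = 2.059. 5.8/2.059 = 2.817; 2.817 − 1.960 = 0.857; Φ(0.857) = 0.804. The exact t calculation gives 0.797. The stated 80% reproduces. The SAP gives no figure for the spline.

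**Step 2: slopes within a recording.** Write y(h) = b0 + b1·h + b2·max(h − k, 0), where h is hours from the start of recording.

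- Knot at the morning dose, k = 0: max(h, 0) = h for every reading, so two columns coincide. The design matrix has rank 2 of 3 and the pre-knot slope cannot be estimated. The post-knot slope can.
- Uniform reduction d: y(h) − d = (b0 − d) + b1·h + b2·max(h − k, 0). Only the intercept moves. With d = 5.8 and k at 6, 12 or 14 h, the fitted effects are −5.8 on the intercept and 0 on both slopes.
- Simulated rejection, knot at 14 h, Day 28 minus baseline: 0.050 and 0.043 for the two slopes, 0.80 for change in level. Level power is 0.94 at SD 8 and 0.75 at SD 11. Across all variations the slope tests stay between 0.040 and 0.065; Monte Carlo error at 1,000 trials is √(0.05 × 0.95/1000) ≈ 0.007.

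**Step 3: recordings joined into one 48-hour series, knot at the join.** Earlier readings now exist. The 5.8 mmHg shift appears as −0.181 mmHg/h before the knot and −0.176 mmHg/h after it. The arms differ after treatment with power 0.60 (0.36 to 0.74 over the variations). They also appear to differ before treatment, with probability 0.61 (0.39 to 0.76), although nobody had yet received product.

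**Step 4: study time, knot at the first dose.** The post-knot slope is −0.211 mmHg/day with no gap between the baseline recording and the first dose, and −0.200 with an assumed 6-day gap. Over 27.5 days these come to −5.80 and −5.49 mmHg. With no gap, power is 0.73 (0.63 to 0.89). This is the difference between two recordings restated per day. The roughly 27 days between them contain no ABPM readings, so a lowess curve cannot locate an inflection there.

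**Step 5: objectives against specified tests.**

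| Secondary ABP objective (SAP 1.1.2.2) | Level test in SAP 4.3.3 |
|---|---|
| Daytime systolic and diastolic | ANCOVA on change in average |
| Nighttime | None; summarised |
| 24-hour | None; summarised |

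SAP 4.3.4 will graph least-squares means by hour and for daytime, nighttime and 24 hours, but 4.3.3 specifies no model that yields the nighttime, 24-hour or hourly ones. No table in SAP 7.1 reports spline coefficients. Table 14.2.4A is titled as a mixed model analysis, yet its shell holds only hourly descriptive statistics.

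**The case against.** The strongest reply is that the sentence is ambiguous and the within-recording reading is not the only one. Start of treatment can be read as the point separating the two recordings. The whole baseline recording then precedes the knot, and a uniform reduction does reach the slopes (Steps 3 and 4). This stands. A reader might infer that no readings precede the knot, or that slopes can never register a reduction; the documents do not support either as a general statement. Even within Day 28, product is applied twice daily, so a knot at the night dose would have earlier readings, although the slopes would still miss a uniform shift. The start-of-test rule quoted above is also only a fallback.

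A second reply is that the first-listed ABP method tests level. This stands too. A reader might infer that a real ambulatory reduction would go unnoticed; for daytime pressure that is wrong, and nighttime and 24-hour changes would at least be tabulated.

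Third, a uniform shift is the effect shape for which within-recording slopes are null by construction, and time course is a legitimate supplementary question. That is fair: slopes could register an effect that varies over the day. But the SAP's stated objectives are mean reductions, and the spline is listed as a way of modelling ABP without a time-course objective of its own.

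Fourth, a chance slope difference taken for a drug effect is ordinary type I error. That is right for a fixed knot. The further knot here is chosen from a graph, without saying whether the arms are pooled, and SAP 3.7 makes no adjustment for multiple endpoints.

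**Conclusion.** The point holds in a limited form. None of the readings examined gives a sound comparison of mean ABP. Within recordings, the knot is undefined at baseline and at the left edge on Day 28, and the effect of a uniform reduction on slopes is exactly zero. Joined recordings produce a false pre-treatment difference. On study time, the slope assumes a steady decline across about 27 unobserved days.

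The zero in the within-recording case is algebraic and depends on no SD. The rejection rates (about 5% for slopes against 75% to 94% for level; 0.36 to 0.89 after treatment for the joint fits) are illustrative, because the level SD is borrowed from the in-clinic plan and the noise and slope SDs are assumed.

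The practical gap is narrower than failure of the ABP analysis: daytime level is tested, while nighttime and 24-hour level are not. The change should be made, but the in-clinic primary analysis is unaffected.

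**What to change.** Replace the slope comparison, or demote it to a descriptive time-course display. In its place, specify a mixed model of hourly mean ABP change (Day 28 minus baseline at the same clock hour), with treatment, clock hour, treatment-by-hour, baseline value at that hour and strata, and a covariance structure named in advance. Report least-squares mean differences with 95% CIs for daytime, nighttime and 24 hours, using the SAP's own clock limits, and show the hourly profile. This follows Protocol 15.3.8, which applies the mixed-model approach to the ambulatory data, and would give Table 14.2.4A the content its title announces.

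If splines are kept, prespecify knots at clock times common to both recordings (8 AM, 4 PM, 10 PM and 6 AM are already in the SAP), state the time axis and how the two recordings are fitted, and compare the baseline-to-Day-28 change in fitted level. Record the change in SAP section 5 before unblinding.

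The cost is SAP text and programming on data already collected, and the loss of the slope contrast as a formal comparison.
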